3.8.2.3 Clinical Global Impression–Global Improvement

The rater will assess (by time point evaluation in comparison with the date of baseline evaluation) improvement of agitation associated with dementia of the Alzheimer's type on an 8-point scale using the CGI-I.

3.8.2.4

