6.4.2 Secondary Endpoint Analyses

The secondary endpoint analysis will be performed on the FAS.

- Changes in CMAI subscales (Aggressive Behavior, Physically Non-aggressive Behavior, and Verbally Agitated Behavior) from baseline at Week 10
- Change in CGI-S related to agitation from baseline to Week 10

The same MMRM analysis as that for the primary endpoint will be performed using the OC dataset.

• CGI-I at Week 10

Each brexpiprazole group will be compared with the placebo group by the Cochran Mantel Haenszel (CMH) Row Mean Scores test with medical care category (inpatient or outpatient) and prior use of antipsychotics (yes or no) as strata using the LOCF dataset. Mean values in each treatment group, differences in mean values between each brexpiprazole group and the placebo group, and their two-sided 95% CIs will be calculated.

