5.4 Handling of Missing Data

The primary analysis of the primary endpoint will be performed in the observed cases (OC) dataset by mixed models for repeated measures (MMRM) without data imputation for missing data under the "missing at random" (MAR) assumption. As a sensitivity analysis for the handling of missing data, placebo multiple imputation and tipping point analysis will be performed under the "missing not at random" (MNAR) assumption. Details are described in Section 8.1.2.

For analyses of efficacy, safety, and other endpoints, the last observation carried forward (LOCF) method (in which missing post-dose data are imputed by the last observed data after initiation of IMP treatment) will be used as needed.

For pharmacokinetic analysis, no imputation will be performed for missing data.

6 Primary and Secondary Outcome Variables

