8.2 Secondary Efficacy Analyses

- Changes in CMAI subscales (Aggressive Behavior, Physically Non-aggressive Behavior, and Verbally Agitated Behavior) from baseline at Week 10
- Change in CGI-S related to agitation from baseline to Week 10
 The same MMRM analysis as that for the primary endpoint will be performed using the OC dataset.

• CGI-I at Week 10

Each brexpiprazole group will be compared with the placebo group by the Cochran Mantel Haenszel (CMH) Row Mean Scores test with medical care category (inpatient or outpatient) and prior use of antipsychotics (yes or no) as strata using the LOCF dataset. Mean values in each treatment group, differences in mean values between each brexpiprazole group and the placebo group based on CMH Row Mean Scores test, and their two-sided 95% CIs will be calculated. The same analysis will be performed on the OC dataset.

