Venous thrombosis in pregnancy

Venous thrombosis limb

Venous thrombosis neonatal

Visceral venous thrombosis

Version: 1.0 Date: 01/06/2023

Appendix 5	List of Summary Tables
CT-1	Subject Disposition (Enrolled Subjects)
CT-2	Reasons for Discontinuation (Randomized Subjects)
CT-3.1.1	Demographic Characteristics (Full Analysis Set)
CT-3.1.2	Demographic Characteristics (Safety Analysis Set)
CT-3.1.3	Demographic Characteristics (Pharmacokinetic Analysis Set)
CT-3.1.3 CT-3.2.1	Baseline Disease Characteristics (Full Analysis Set)
	• • • • • • • • • • • • • • • • • • • •
CT-3.2.2	Baseline Disease Characteristics (Safety Analysis Set)
CT-4.1.1	Concomitant Medications (Antipsychotic): Medications Taken Prior to Start of Study Therapy (Safety Analysis Set)
CT-4.1.2	Concomitant Medications (Antipsychotic): Medications Taken During Study Therapy (Safety Analysis Set)
CT-4.1.3	Concomitant Medications (Antipsychotic): Medications Taken Post Study Therapy (Safety Analysis Set)
CT-4.2.1	Concomitant Medications (Antidementia Drug): Medications Taken Prior to Start of Study Therapy (Safety Analysis Set)
CT-4.2.2	Concomitant Medications (Antidementia Drug): Medications Taken During Study Therapy (Safety Analysis Set)
CT-4.2.3	Concomitant Medications (Antidementia Drug): Medications Taken Post Study Therapy (Safety Analysis Set)
CT-4.3.1	Concomitant Medications (Other): Medications Taken Prior to Start of Study Therapy (Safety Analysis Set)
CT-4.3.2	Concomitant Medications (Other): Medications Taken During Study Therapy (Safety Analysis Set)
CT-4.3.3	Concomitant Medications (Other): Medications Taken Post Study Therapy (Safety Analysis Set)
CT-4.4	Summary of Major Protocol Deviations by Center and Type of Deviation (Randomized Subjects)
CT-5.1	Summary of Efficacy Results at Week 10 (Full Analysis Set)
CT-5.2	Summary of Mean Change From Baseline to Double Blind Treatment Period by Study Week in CMAI Total Score - MMRM (Full Analysis Set)
CT-5.3	Summary of Mean Change From Baseline to Double Blind Treatment Period by Study Week in CMAI Subscale Score - MMRM (Full Analysis Set)
CT-5.4	Summary of Mean Change From Baseline to Double Blind Treatment Period by Study Week in CGI-S Scale - MMRM (Full Analysis Set)
CT-5.5.1	Summary of Mean CGI-I Score by Study Week in Double Blind Treatment Period Relative to Baseline - LOCF (Full Analysis Set)
CT-5.5.2	Summary of Mean CGI-I Score by Study Week in Double Blind Treatment Period Relative to Baseline - OC (Full Analysis Set)
CT-5.6.1	

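### The lead CGI-I analysis at Week 10 uses LOCF, while the other secondary endpoints use MMRM under MAR; a MAR-consistent lead analysis would be better and costs little

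*SAP*

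**What the plan says.** SAP 8.2 handles the secondary endpoints in two ways.

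- **CMAI subscales and CGI-S:** "The same MMRM analysis as that for the primary endpoint will be performed using the OC dataset". SAP 5.4 states that the primary MMRM makes no imputation and assumes MAR.
- **CGI-I at Week 10:** each brexpiprazole group is compared with placebo by the CMH row mean scores test, with the two stratification factors "as strata using the LOCF dataset". The section then adds: "The same analysis will be performed on the OC dataset". SAP Appendix 5 gives each version its own table (CT-5.5.1 and CT-5.5.2).

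Protocol 6.4.2 has only the LOCF version for CGI-I: "prior use of antipsychotics (yes or no) as strata using the LOCF dataset".

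SAP 5.4 describes LOCF as a method "in which missing post-dose data are imputed by the last observed data after initiation of IMP treatment". It sets no minimum exposure. Protocol Table 3.8-1 schedules CGI-I at Weeks 2, 4, 6, 8 and 10 or at discontinuation. Protocol 3.8.2.3 has it rated "on an 8-point scale using the CGI-I", relative to baseline, so it has no baseline value of its own. SAP 3.2 moves the 2 mg group to 2 mg only after the Week 2 evaluation; the 1 mg group reaches its dose after the Week 1 evaluation.

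**The concern.** LOCF enters a dropout's last rating as if it had been observed at Week 10. If improvement builds over the treatment period, that rating understates what the plan wants to estimate, and the error is larger in the arm that loses more subjects or loses them earlier. For a 2 mg subject last rated at or before Week 2, the carried value reflects at most 1 mg. Protocol 3.2.3 itself argues that time at 2 mg is needed before efficacy can be judged.

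Dropout could differ by arm. Dose reduction is not allowed and tolerability problems end treatment (SAP 3.2), while lack of efficacy and worsening agitation are also reasons to leave (protocol 3.9.3.2).

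The observed-case run does not close the gap. It uses only subjects rated at Week 10 and ignores the earlier ratings of everyone else, whereas an MMRM uses them. The imputation analyses in SAP 8.1.2 are for the primary endpoint, and none is listed for CGI-I. At stake is a named secondary result that could differ from CMAI and CGI-S only because its missing data were handled differently.

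**Working it through.** **The plan's own figures.** No power or sample size is stated for CGI-I. The stated powers concern CMAI (difference 5.35, SD 15.06, two-sided 5%). The noncentral t-test has noncentrality 5.35 / [15.06 × √(1/n₁ + 1/n₂)]. This is 3.06 for 148 vs 148 and 2.83 for 148 vs 111, giving powers of 86.1% and 80.5%. Both match, and neither depends on CGI-I.

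**Inputs for CGI-I (all assumed).**
- Mean score moves from 4 to 3.2 on placebo (improvement P = 0.8) and to 2.8 on drug (D = 1.2). The true difference is 1.2 − 0.8 = 0.40.
- Improvement is linear over 10 weeks, so a subject last rated at week w has achieved the fraction f = w/10.
- Dropout proportions are d_D (drug) and d_P (placebo), and dropouts follow their arm's mean curve.

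**Formula.** LOCF difference = D[(1 − d_D) + f·d_D] − P[(1 − d_P) + f·d_P].

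**Example, Week 4 (f = 0.4).**
- 20% in both arms: 1.2 × 0.88 − 0.8 × 0.88 = 1.056 − 0.704 = 0.352.
- 15% placebo, 25% drug: 1.2 × 0.85 − 0.8 × 0.91 = 1.020 − 0.728 = 0.292.
- 25% placebo, 15% drug: 1.2 × 0.91 − 0.8 × 0.85 = 1.092 − 0.680 = 0.412.

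| Last rating | 20% both arms | 15% placebo, 25% drug | 25% placebo, 15% drug |
|---|---|---|---|
| Week 4 | 0.352 (−12%) | 0.292 (−27%) | 0.412 (+3%) |
| Week 6 | 0.368 (−8%) | 0.328 (−18%) | 0.408 (+2%) |
| Week 8 | 0.384 (−4%) | 0.364 (−9%) | 0.404 (+1%) |

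If every dropout were last rated at Week 2 (f = 0.2), the same formula gives 0.336 (−16%), 0.256 (−36%) and 0.416 (+4%). That is an extreme, not an expectation.

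**Direction.** The error in the difference is (1 − f)(P·d_P − D·d_D). With these inputs it favours drug only when placebo dropout exceeds D/P = 1.5 times drug dropout.

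**Check with a different response shape.** Let scores approach the Week 10 mean exponentially (time constant 2 or 4 weeks), with SD 1.2, 148 per arm, a normal approximation, and dropout timing from all at Week 2 to mostly late. For a true difference of −0.40 (lower scores are better), LOCF gives:
- 10% or 20% in both arms: −0.35 to −0.40.
- 20% drug, 10% placebo: −0.31 to −0.39.
- 30% drug, 10% placebo: −0.24 to −0.38.
- 10% drug, 20% placebo: −0.40 to −0.42.

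With no true difference, rejection stays at 5.0% when dropout is equal. It is 5.1-10.0% at 30% drug vs 10% placebo, with the bias against drug, and 5.0-6.2% at 10% vs 20%, with the bias towards drug.

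**The case against.** The strongest defence has four parts.

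1. **Little depends on CGI-I.** The fixed-sequence procedure covers only the two dose comparisons on the primary endpoint, and the sample size rests on CMAI. CGI-S, the companion global rating at the same visits, already uses MMRM. This stands and limits the consequence.
2. **The result does not rest on LOCF alone.** The observed-case run has its own table, and SAP 8.4.2 analyses CGI-I at each time point. These would help to expose a result driven by carried-forward values. They do not supply an estimate under MAR.
3. **The test suits the scale.** CGI-I is ordinal and has no baseline, so a stratified row-mean-score test is defensible. This stands, but it defends the test and not the imputation. The same test can follow multiple imputation.
4. **The bias is modest and mostly works against drug.** This is true under equal or late dropout. It becomes material when dropout is early and heavier on drug, and the documents give no rates that rule this out.

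Two stronger readings are tempting but unsupported. A reader might infer that titration-phase ratings generally stand in for Week 10. That applies only to subjects last rated at or before the Week 2 evaluation. CGI-I is also rated at discontinuation, later dropouts carry later values, and SAP 3.4 assigns any rating on Days 65-78 to Week 10. A reader might also infer that every other continuous efficacy endpoint uses MMRM. CGI-I is ordinal and the exploratory methods are redacted, so only CMAI total, its subscales and CGI-S can be confirmed.

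**Conclusion.** The point holds as a worthwhile, inexpensive improvement. The lead CGI-I analysis treats carried-forward ratings as Week 10 data, and no listed CGI-I analysis handles missing values under the MAR assumption applied to the other secondary endpoints.

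Under the linear assumptions, with last ratings between Weeks 4 and 8, LOCF weakens a 0.40 difference by 4-12% with equal 20% dropout. The loss is 9-27% when drug dropout is 25% and placebo dropout 15%. With those rates reversed, LOCF strengthens the difference by 1-3%. All of these sizes depend on assumed response curves, dropout rates and dropout timing.

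A reader might infer a risk to the trial's main claim or a large risk of a false positive. Neither is supported: the primary conclusion does not use CGI-I, and where the bias favoured drug the calculated rejection rate was at most 6.2%.

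**What to change.** In SAP 8.2, make one of these the main CGI-I analysis, before data lock:

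- **MMRM** on CGI-I scores at Weeks 2, 4, 6, 8 and 10, built as for the other secondary endpoints, with baseline CGI-S and its interaction with visit as covariates; or
- **multiple imputation under MAR**, followed by the planned CMH row mean scores test. This keeps the ordinal-score test. SAP 8.1.2.2 already pairs MAR imputation with a stratified rank test for CMAI.

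Keep the CMH test on LOCF and observed-case data as sensitivity analyses. Record the departure from protocol 6.4.2 in SAP Section 15.

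No new data are needed. The cost is a new model specification, because the code in SAP 8.1.3 models change from the same scale's baseline and CGI-I has none. The MMRM also treats an ordinal score as continuous, as the plan already does for CGI-S. The imputation route avoids that but needs an imputation model and a pooling rule written for CGI-I.

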8.3 Subgroup Analyses

The same MMRM analysis as that for the primary endpoint will be performed on the change in CMAI total score from baseline for each of the subgroup categories within each of the following items using the OC dataset (in the subgroup analyses of medical care category and prior use of antipsychotics, those particular factors will be excluded from the respective analysis models). For CYP2D6 phenotype, all subjects in the placebo group will be included in each subgroup.

- Medical care category (inpatient, outpatient)
- Prior use of antipsychotics (yes or no)
- Type of caregiver (hospital staff, care facility staff, family)
- Sex (male, female)
- Age $(< 80, \ge 80)$ $(< 65, \ge 65 \text{ to } < 75, \ge 75)$
- CMAI total score at baseline (≤ median or > median)
- Body weight (\leq median, > median)
- BMI (\leq median, > median)
- CYP2D6 phenotype (IM, EM)

- Impact of COVID-19 pandemic (subjects who completed/discontinued the trial before 07 Apr 2020, subjects who completed/discontinued the trial on or after 07 Apr 2020)
- Concomitant use of antidementia drugs (yes or no)

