9	 Patients who have shown verbal aggression or physical aggression for 3 times or more during the 2 weeks before baseline evaluation. Examples of verbal aggression and physical aggression include the following symptoms in the "Consensus provisional definition of agitation in cognitive disorders" of IPA.^a Verbal aggression: yelling, speaking in an excessively loud voice, using profanity, screaming, shouting, etc.
	• Physical aggression: grabbing, shoving, pushing, resisting, hitting others, kicking objects or people, scratching, biting, throwing objects, self-hitting, slamming doors, tearing things, destroying property, etc.
10	Patients who show significant improvement (of two grades or more) in CGI-S from screening to baseline evaluation.
11	Patients who show inadequate response to nonpharmacological therapy for agitation associated with dementia of the Alzheimer's type or who are otherwise judged to be in need of pharmacological therapy.
12	Patients who are either capable of walking on their own or are able to move about with the use of a walking aid (a walker or wheelchair) and whose vision and hearing are sufficient to enable the required tests and observations for the trial (the use of glasses, hearing aids, etc, is acceptable).

^a Cummings J, Mintzer J, Brodaty H, Sano M, Banerjee S, Devanand DP, et al. Agitation in cognitive disorders: International Psychogeriatric Association provisional consensus clinical and research definition. International Psychogeriatrics. 2015;27:7-17.

[Rationale for inclusion criteria]

- This criterion is specified for ethical considerations. 1.
- 2. This criterion is specified because DSM-5 is recommended in the Practice Guideline for Dementia 2017, and NINCDS-ADRDA is widely used in clinical trials for dementia of the Alzheimer's type. These standards have been established as the diagnostic standards for dementia of the Alzheimer's type.
- 3. Although it is known that most patients with dementia of the Alzheimer's type are above the age of 65, there is a small number of patients below the age of 65. Past trials have suggested that patients of ages 55 and above may be suitable for such trials. Thus, the lower age limit was set at 55. On the other hand, given that patients aged over 90 could interfere with the evaluations set for this trial and in consideration of safety, 20 the upper age limit was set at 90.

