6.4.5 Subgroup Analyses

The same MMRM analysis as that for the primary endpoint will be performed on the change in CMAI total score from baseline to Week 10 for each of the subgroup

categories within each of the following items using the OC dataset (in the subgroup analyses of medical care category and prior use of antipsychotics, those particular factors will be excluded from the respective analysis models).

- Medical care category (inpatient or outpatient)
- Prior use of antipsychotics (yes or no)
- Type of caregiver (hospital staff, care facility staff, family, or other)
- Sex (male or female)
- Age (< 80 or \ge 80)
- CMAI total score at baseline (< 56 or \geq 56)
- •
- Body weight (\leq median or > median)
- Body mass index (BMI) (\leq median or > median)

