3.5.10 Mini-Mental State Examination (MMSE)

The MMSE total score will be the sum of scores for MMSE Items 1 through 30.

4 Sample Size

In Trial 331-12-283, which was performed outside Japan, the 2 mg fixed-dose group showed superiority over the placebo group in patients with aggression (patients with aggressive behavior at baseline), thus suggesting that it may also be the optimum dose for Japanese patients. Efficacy was not observed in the 1 mg fixed-dose group, but in Trial 331-12-284, the efficacy of a dose less than 2 mg was suggested by the results obtained in patients from the flexible-dose (0.5 to 2 mg) group, who had aggression.

In this trial, a power of detection $\geq 80\%$ will be achieved for comparison between the placebo group and the 1 mg group to allow evaluation of superiority over the placebo group if equivalent efficacy is demonstrated in the 1 and 2 mg groups. For comparison between the 2 mg group (possible optimum dose) and the placebo group, a more sufficient power of detection will be obtained by changing the randomization ratio. In this trial, it is assumed that the difference between the 2 mg group and the placebo group in the change in the CMAI total score from baseline to Week 10 is -5.35, and the standard deviation (calculated from the standard error of the difference between the 2 mg and placebo groups and the number of subjects at baseline) is 15.06 on the basis of the results of Trial 331-12-283. By setting the number of subjects in the 2 mg group, 1 mg group, and placebo group as 148, 111, and 148, respectively (randomization ratio of 4:3:4), the power of detection is 86.1% for the comparison between the 2 mg group and the placebo group and is 80.5% for the comparison between the 1 mg group and the placebo group in a test with a significance level of 5% (two sided).

On the basis of the above considerations, the number of subjects will be set at 148 in the 2 mg group, 111 in the 1 mg group, and 148 in the placebo group (randomization ratio of 4:3:4).

5 Statistical Analysis Datasets

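### Subgroup effects come from separate MMRMs with no estimate of the difference between categories, so an even split of one uniform effect would often give one significant and one non-significant half

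*SAP*

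**What the plan says.** SAP 8.3 sets the subgroup method in one sentence: "The same MMRM analysis as that for the primary endpoint will be performed on the change in CMAI total score from baseline for each" category within every listed factor, on observed cases. Where the factor is itself a model term (care category, prior antipsychotics), that term is dropped. Protocol 6.4.5 agrees: "The same MMRM analysis as that for the primary endpoint will be performed on the change in CMAI total score from baseline to Week 10", again category by category.

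SAP 8.3 shows ten two-level and two three-level classifications, 10 × 2 + 2 × 3 = 26 categories. Baseline CMAI, body weight and BMI are split at the median. For CYP2D6 phenotype, the whole placebo group is used in both categories.

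No treatment-by-subgroup term appears in the SAS code of SAP 8.1.3. SAP 15, which lists changes to the planned analyses, adds none. Tables CT-6.1.1 to CT-6.12.2 give one table per category and none that compares categories. One factor (CT-6.7.x) is not visible in the public version, but the stated method covers every factor.

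**The concern.** A subgroup analysis asks whether the effect differs between categories. The plan produces a dose-placebo difference and interval inside each category and stops there. The natural reading is then to see which intervals exclude zero, and a subgroup is much smaller than the trial that was sized. A uniform effect can therefore look like an effect in one category and none in the other, with nothing in the output to correct that reading.

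The separate fits add a second difficulty. Each re-estimates 15 covariance parameters (five visits, unstructured) and 22 mean parameters (1 intercept, 2 treatment, 4 visit, 1 baseline, 8 treatment by visit, 4 baseline by visit, 1 care category, 1 prior antipsychotics) from one category alone. One category is age below 65. On that age range protocol 3.4.2 notes that "there is a small number of patients below the age of 65", a remark about the disease population rather than about expected enrolment.

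**Working it through.** **Inputs (SAP 4, Sample Size).** Two-sided 5% test. The assumed 2 mg-placebo "change in the CMAI total score from baseline to Week 10 is -5.35". The SD "is 15.06 on the basis of the results of Trial 331-12-283". Group sizes are "148 in the 2 mg group, 111 in the 1 mg group, and 148 in the placebo group". The 1 mg power takes the same difference, for the case "if equivalent efficacy is demonstrated in the 1 and 2 mg groups".

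**Method.** Two-sample noncentral t, as an approximation to the Week 10 MMRM contrast.

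**Step 1: reproduce the plan.** 148 v 148 gives 86.1% and 111 v 148 gives 80.5%, as stated in SAP 4.

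**Step 2: even split, uniform effect.** With 74 v 74 per half, SE = 15.06 × √(2/74) = 2.48 and power is 57.4%. The halves contain different patients, so:
- both significant: 0.574² = 33%
- neither significant: 0.426² = 18%
- exactly one significant: 2 × 0.574 × 0.426 = 48.9%

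For 1 mg (55.5 v 74 per half), power is 51.0% and exactly one is significant 50.0% of the time.

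**Step 3: vary the assumptions (2 mg).** For splits with powers a and b, P(exactly one) = a(1−b) + b(1−a).

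| True effect in both categories | Split | Power a, b | Exactly one significant |
|---|---|---|---|
| 5.35 | 50/50 | 57%, 57% | 49% |
| 4 | 50/50 | 36%, 36% | 46% |
| 7 | 50/50 | 80%, 80% | 32% |
| 5.35 | 70/30 (assumed) | 72%, 38% | 55% |
| 5.35 | 80/20 (assumed) | 78%, 27% | 63% |

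Only the three median splits are even by construction. The documents give no shares for the other factors, so the 70/30 and 80/20 rows are assumptions. Patient loss hardly matters: with 10% or 20% loss at an even split, the normal approximation gives 49.7% and 50.0%, against 48.7% with none.

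**Step 4: CYP2D6.** The shared placebo group makes the two results positively correlated. Simulation (one million draws, normal approximation, splits 50/50 to 70/30) gives 33% to 40% for 2 mg and 39% to 45% for 1 mg.

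**Step 5: what a contrast would show.** At an even split, the SE of the difference between the two 2 mg effects is √2 × 2.48 = 3.50, so the 95% CI is ±1.96 × 3.50 = ±6.9 points. In simulation with a uniform effect, this contrast rejects 5% of the time. It is significant in only about 10% of the pairs in which one half is significant and the other is not.

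**The case against.** The strongest reply is that the harm is not in the plan. The fixed sequence in SAP 8.1.1 covers only the two primary comparisons. Subgroup results have no threshold or decision role, and neither document says a subgroup will be called positive or negative. This stands. A reader might infer that error control is weakened or that subgroup claims are intended; the documents support neither.

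A reader might also infer that about half of all the two-level factors will show such a split. That goes too far. The figure is a per-factor probability at the design effect and a near-even split. CYP2D6 is lower. The same patients enter every factor, so the realised count can vary widely.

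Nor is it right that effects could be compared only by setting p-values side by side. Except for CYP2D6, the categories of a factor are disjoint, so the difference and its SE can be worked out from the planned intervals. What is missing is a planned row and a rule for reading it, not the information.

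The plan is not silent on small categories either. The same MMRM brings with it the SAP 8.1.1 fallback: heterogeneous Toeplitz, then autoregressive, then compound symmetry, with a sandwich estimator. The limit of this is that two categories of one factor could be reported under different covariance structures and SE estimators.

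Finally, the contrast is weak. If the effect differed by a full 5.35 points between halves, 5.35/3.50 = 1.53 gives power of about 33%. That also stands. It is a reason to report the contrast as an interval and to warn against reading non-significance as sameness.

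**Conclusion.** The gap is real: the plan has no estimate of whether the effect differs between categories. At the design inputs, an even split of a uniform effect gives one significant and one non-significant half 49% of the time for 2 mg and 50% for 1 mg. For 2 mg the figure falls to about 32% if the true effect is 7 points, and rises to 55-63% for the assumed uneven splits at the design effect. These figures rest on the two-sample approximation, an SD of 15.06 in every category, and independent categories. Primary inference is untouched, so this is an inexpensive improvement to reporting and not a defect in the confirmatory analysis.

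**What to change.** Keep the CT-6.x displays. For each factor except CYP2D6, add to SAP 8.3 the Week 10 difference between categories in the dose-placebo effect, for each dose, with its 95% CI. For a three-level factor, name the reference category. There are two ways to obtain it:
- **From the separate fits:** subtract the two estimates, with SE = √(SE₁² + SE₂²). This is valid because the categories are disjoint.
- **From one FAS model:** add subgroup, subgroup by visit, treatment by subgroup, and treatment by subgroup by visit. This assumes a common covariance and common covariate effects across categories. The covariate assumption needs most care for the baseline CMAI split, where the subgroup is a function of the model's own covariate.

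Choose one in advance. State that significance within a category, or its absence, is not evidence of a different effect, and that a non-significant contrast is not evidence of a uniform one. For CYP2D6, keep the separate display without a contrast. Note beside small categories, such as age below 65, which covariance structure was used.

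The cost is SAP wording and a little programming. The added intervals will be wide, about ±6.9 points for 2 mg at an even split against a planned effect of 5.35, and the text should say so.
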